7.1.6. Monitoring for Potential Immune Mediated Endocrinopathies

Participants will be monitored for clinical signs and symptoms of hypophysitis, adrenal insufficiency (including Addisonian crisis), and hyper- or hypothyroidism. Laboratory evaluation will be performed as clinically indicated based on symptoms. For example, the development of symptoms of adrenal insufficiency, such as unexplained nausea, vomiting and hypotension, would trigger prompt evaluation (Cosyntropin Stimulation Testing) and treatment (systemic glucocorticoids). Symptoms suggestive of an inflammatory pituitary process with mass effect, such as diplopia, visual field abnormalities and severe headache, call for urgent pituitary imaging and evaluation for hypopituitarism, with specific attention to the pituitary-adrenal axis. Symptoms of disordered thyroid metabolism, such as changes in bowel frequency, fatigue, unexplained weight loss or gain should prompt evaluation of thyroid function tests, with a focus on free thyroid hormone levels (T3 and T4) given the possibility that thyroid stimulating hormone levels may be unreliable due to immune-mediated pituitary dysfunction.

7.1.7. Acetylcholine Receptor Testing

A blood sample will be collected at screening for central evaluation of acetylcholine receptor (AChR) antibodies. **CCI** [REDACTED]

[REDACTED] treatment decisions will be made based on the clinical diagnosis. The evaluation for AChR antibodies is included to exclude participants who test positive at screening as agreed upon with the US FDA and to confirm requirement for evaluation if myasthenia gravis is suspected.⁹⁹

7.1.8. Cardiac Safety Monitoring

The algorithm for cardiac Safety Monitoring is shown in [Figure 2](#) below.

[figure not shown]
For participants undergoing screening, circulating levels of cardiac Troponin-I (cTnI) must be measured and found to be within the normal reference range within 28 days before study entry, preferably using the central laboratory kits provided. Dosing should not proceed until results within the normal reference range have been received by the Investigator. For any results above of the normal reference range (even if borderline), the participant should be referred to a cardiologist by the Investigator for complete cardiac workup and repeat cardiac troponin. The participant can only enter the study after cardiac evaluation, troponin findings within the normal reference range, cardiac clearance, and the Sponsor's approval.

For participants ongoing in the study, circulating levels of cardiac Troponin-I (cTnI) must be measured within 10 days of dosing on the days shown in the [SOA](#) (ie, C1D29, C1D57, C1D85, C2D29, month 9 and month 12) and found to within the normal reference range. No dosing of participants can occur unless the cTnI is within the normal reference range. For any results above the normal reference range (even if borderline) the participant must be referred by the Investigator to a cardiologist for complete work-up and repeat cTnI. Dosing

can only occur after cardiac evaluation, cTnI findings within the normal reference range, cardiac clearance, and the Sponsor's approval.

While central laboratory testing for cTnI is preferred, it requires a minimum of 3 days to return results. Therefore, local laboratory testing of cTnI may be used, but only if the timing of measuring cTnI by the central laboratory test (minimum 3 day turnaround time) puts an undue burden or risk on the participant. The use of cardiac troponin-T is strongly discouraged, but could be used in place of cTnI if the central laboratory test puts an undue burden or risk on the participant.

Figure 2. Cardiac Safety Monitoring Algorithm

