primary sclerosing cholangitis are excluded; however, non-immune mediated gastroesophageal reflux disease (esophagitis/gastritis) under treatment with proton pump inhibitors is allowed (assuming no drug interaction potential).

12. Acetylcholine receptor binding antibody ≥ 0.5 nmol/L.
13. Abnormal neurologic examination at screening indicating possible underlying autoimmune disorder(s).
14. Any of the following in the previous 12 months or currently: myocardial infarction, severe/unstable angina, coronary/peripheral artery bypass graft, symptomatic congestive heart failure, cerebrovascular accident, transient ischemic attack or symptomatic pulmonary embolism, as well as ongoing cardiac dysrhythmias of NCI CTCAE Grade ≥ 2 , atrial fibrillation of any grade, or QTc interval > 470 msec at screening.
15. Cardiac Troponin-I (cTnI) must be measured and found to be within the normal reference range before the administration of the first dose. Abnormal circulating levels of cTnI are exclusionary.
16. Individuals in whom a skin-fold measurement of the cutaneous and subcutaneous tissue for 2 or more eligible injection sites exceeds 50 millimeters (mm).
17. Bleeding diathesis or condition associated with prolonged bleeding time that would contraindicate IM injection.
18. Current use of any implanted electronic stimulation device, such as cardiac demand pacemakers, automatic implantable cardiac defibrillator, nerve stimulators, or deep brain stimulators.
19. Presence of any surgical or traumatic metal implants at the site of administration (medial deltoid muscles or overlying skin or vastus lateralis muscle).
20. Hypertension that cannot be controlled by medications ($> 150/100$ mmHg despite optimal medical therapy).
25. Severely symptomatic Chronic Obstructive Pulmonary Disease (eg, requiring ambulatory oxygen).
21. Participation in other studies involving investigational drug(s) within 4 weeks prior to study entry.
22. Known or suspected hypersensitivity to any of the VBIR-2 components.
23. Other acute or chronic medical or psychiatric condition, including recent (within the past year) or active suicidal ideation or behavior or laboratory abnormality that may increase the risk associated with study participation or investigational product administration or may interfere with the interpretation of study results and, in the

judgment of the investigator, would make the participant inappropriate for entry into this study.

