Non-hematologic	Continue at the same dose level.	For pneumonitis, endocrinopathy, colitis, creatinine, AST, ALT, or total bilirubin elevations, withhold dose until toxicity is Grade ≤ 1 , or has returned to baseline, then resume at the same dose level or reduce by 1 level (considering each compound separately) at the discretion of the investigator. For all other events, continue at the same dose level.	For pneumonitis, colitis, endocrinopathy, creatinine, AST, ALT or total bilirubin elevations, or pruritus discontinue treatment.** For all other events withhold dose until toxicity is Grade ≤ 1 , or has returned to baseline, then resume treatment at the same dose level or reduce the dose by 1 level (considering each compound separately) at the discretion of the investigator.* Treatment may resume with VBIR-2 with an interruption of sasanlimab for one dose at the discretion of the investigator.	Discontinue treatment.**
Hematologic	Continue at the same dose level.	Continue at the same dose level.	Withhold dose until toxicity is Grade ≤ 2 , or has returned to baseline, then resume treatment at the same dose level.	Discontinue treatment.**

* Nausea, vomiting, or diarrhea must persist at Grade 3 despite maximal medical therapy to require dose modification.

** For Grade ≥ 3 colitis or pneumonitis, discontinue treatment permanently. For any grade of myocarditis discontinue treatment permanently. For all other conditions participants may be allowed to remain in the study to receive the VBIR-2 2 after the toxicity is Grade ≤ 1 or returned to baseline, and only if agreed upon by the Investigator and Sponsor.

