New onset of cardiac signs or symptoms and / or new laboratory cardiac biomarker elevations (eg, troponin, CK-MB, BNP) or cardiac imaging abnormalities suggestive of myocarditis.	
 -Withhold study treatment. -Hospitalize. -In the presence of life threatening cardiac decompensation, consider transfer to a facility experienced in advanced heart failure and arrhythmia management. -Consult cardiologist to establish etiology and rule-out immune-mediated myocarditis. -Guideline based supportive treatment as per cardiology consult.* -Consider myocardial biopsy if recommended per cardiology consult. 	
 -If symptoms improve and immune-mediated etiology is ruled out, restart study treatment. -If symptoms do not improve/worsen, viral myocarditis is excluded, and immune-mediated etiology is suspected or confirmed following cardiology consult, manage as immune-mediated myocarditis.
Immune-mediated myocarditis.	
 -Permanently discontinue study treatment. -Guideline based supportive treatment as appropriate as per cardiology consult.* 1.0 to 2.0 mg/kg/day prednisone or equivalent. -Add prophylactic antibiotics for opportunistic infections. 	
Once improving, taper steroids over at least 1 month.
 
If no improvement or worsening, consider additional immunosuppressants (eg, azathioprine, cyclosporine A).

*Local guidelines, or eg. ESC or AHA guidelines

ESC guidelines website: <https://www.escardio.org/Guidelines/Clinical-Practice-Guidelines> AHA guidelines website:

http://professional.heart.org/professional/GuidelinesStatements/UCM_316885_Guidelines-Statements.jsp.

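### After an on-study troponin rise, Section 7.1.8 and Appendix 5 set different conditions for resuming treatment, and no readable text says which governs

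*Protocol*

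**What the plan says.** Section 7.1.8 deals with participants already on study. Its trigger is a laboratory value, with or without symptoms: "For any results above the normal reference range (even if borderline) the participant must be referred by the Investigator to a cardiologist". It then states a flat bar, "No dosing of participants can occur unless the cTnI is within the normal reference range", and closes by saying that dosing "can only occur after cardiac evaluation, cTnI findings within the normal reference range, cardiac clearance" and sponsor approval.

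Appendix 5 has two Cardiac rows. The first, in a block headed for myocarditis, lists among its triggers "new laboratory cardiac biomarker elevations (eg, troponin, CK-MB, BNP" and similar markers. The initial steps are to withhold treatment, hospitalize, and have a cardiologist establish the cause. The follow-up instruction is: "If symptoms improve and immune-mediated etiology is ruled out, restart study treatment". The second row, for immune-mediated myocarditis, discontinues treatment permanently.

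Section 5.4.5.3, in the double-asterisk footnote to Table 12, adds: "For any grade of myocarditis discontinue treatment permanently". By its title, the table covers toxicity related to sasanlimab and/or tremelimumab.

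**The concern.** Two current parts of the protocol speak to the same event, a newly raised troponin during treatment, and give different lists of what must be true before the next dose. A site that works from Appendix 5 can satisfy every condition there and still be in breach of Section 7.1.8.

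The matter is one of participant safety. Troponin testing was added in Amendment 1 to mitigate the risk of myocarditis. Safety and tolerability are a primary objective of Part 2, and Section 9.7 provides for no data monitoring committee. Section 7.1.8 names six on-study cTnI time points: C1D29, C1D57, C1D85, C2D29, Month 9 and Month 12. Dosing also takes place at C2D1, C2D57, C2D85, Months 10 and 11, and after Month 12. A restart under Appendix 5 at one of those visits would meet no scheduled test that brought the discrepancy to light.

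**Working it through.** The plan states no figure on this point and no arithmetic applies, so the check is a comparison of trigger and resumption condition.

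| | Section 7.1.8 | Appendix 5, first Cardiac row |
|---|---|---|
| Trigger | Any cTnI above normal, borderline included | New cardiac signs or symptoms, new biomarker elevation (troponin named), or imaging abnormality; no cut-off given |
| Immediate action | Cardiology referral, full work-up, repeat cTnI; no dosing | Withhold, hospitalize, cardiology consult |
| cTnI back to normal before dosing | Required | Not mentioned |
| Cardiac clearance | Required | Not mentioned |
| Sponsor approval | Required | Not mentioned |
| Symptoms improved | Not mentioned | Required |
| Immune-mediated cause ruled out | Not mentioned as such | Required |

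Applied to the possible courses of a raised on-study cTnI:

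1. **The rise is not thought to suggest myocarditis.** Only Section 7.1.8 clearly applies. There is one instruction and no conflict.
2. **Worked up as possible myocarditis; symptoms improved, immune cause ruled out, but cTnI still above normal or sponsor approval not given.** Section 7.1.8 forbids dosing and Appendix 5 says restart. The instructions are opposite.
3. **As in 2, but the participant never had symptoms.** Section 7.1.8 gives a complete rule. Appendix 5 makes improvement of symptoms a condition, and there are none to improve, so it gives no usable rule.
4. **Immune-mediated myocarditis.** The second Cardiac row and the Table 12 footnote both discontinue permanently. Section 7.1.8 sets only necessary conditions for dosing, so it contradicts neither.
5. **Myocarditis judged not immune-mediated, for example viral, with symptoms improved.** Appendix 5 says restart. Read on its own words, the Table 12 footnote says stop permanently. Read within the table's title, it may not apply at all. The text does not settle which reading is meant.

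As to precedence, Section 7.1.8 does not cite Appendix 5, and the Cardiac rows do not cite Section 7.1.8. Sections 5.4.5.2 and 5.4.5.3 point to Appendix 5 for pulmonary, gastrointestinal, liver, endocrine, skin, neurological and renal toxicity. They do not list cardiac.

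**The case against.** The best defence is that the protocol already routes the reader. The troponin footnotes in the Schedules of Activities refer to Section 7.1.8 for details, the bar there is categorical, and nothing in Appendix 5 waives it. The two texts can be applied together, with Appendix 5 adding conditions and removing none. The Appendix 5 row may also be narrower, since it sits under a myocarditis heading and speaks of findings that suggest myocarditis. Figure 2, the cardiac monitoring algorithm, is not shown in the copy reviewed and may link the steps.

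Part of this stands. The passages can be combined, and a careful site might do so. But the text does not tell it to, and the Appendix 5 line is an unqualified instruction to restart. The qualifier about suggesting myocarditis can be read as attached to imaging alone, in which case an isolated troponin rise is enough to enter the row. Whatever Figure 2 shows, the restart sentence remains as written.

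Three stronger readings are tempting and are not supported:

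- A reader might infer that one troponin result leads to three different dosing decisions, with Table 12 as the third. The footnote acts on a diagnosis of myocarditis, never mentions troponin, sits in a related-toxicity table introduced as general rules from which action may differ, and agrees with Appendix 5 on immune-mediated cases.
- A reader might see the same conflict at screening, because Part 2 exclusion 15 says "Abnormal circulating levels of cTnI are exclusionary" while Section 7.1.8 allows entry after work-up and a normal repeat. Both require a normal cTnI before the first dose, and exclusion 15 does not forbid a repeat test, so they can be read together.
- A reader might size the problem by counting every elevated cTnI. The conflict needs improved symptoms, an immune cause ruled out, and a cTnI still raised or sponsor approval missing. That is a subset of elevated results, and the documents give no rate for it or for elevated results in general.

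**Conclusion.** The concern holds between Section 7.1.8 and the first Cardiac row of Appendix 5. Their resumption conditions differ on three items (normal cTnI, cardiac clearance, sponsor approval), and at least one foreseeable participant state produces opposite instructions. The Appendix 5 condition on symptoms also leaves an asymptomatic rise without a usable rule. The scope of the Table 12 footnote for non-immune myocarditis is a lesser ambiguity.

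No count of affected participants can be given. Part 2 plans about 30 participants, and a single one re-dosed against Section 7.1.8 would be enough to matter. The conclusion rests on the readable text and assumes that Figure 2 does not alter the Appendix 5 restart line. It takes no view on which clinical rule is right.

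**What to change.** Reconcile the conditions for resuming treatment in Section 7.1.8 and in the first Cardiac row of Appendix 5, including how they apply to a troponin rise without symptoms. Cross-reference the two places, state which governs if they differ, and check that Figure 2 shows the same conditions. State whether the Table 12 footnote covers myocarditis that is not immune-mediated, and align it with Appendix 5. The clinical content is for the sponsor and its cardiology advisers to decide.

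The cost is protocol wording in a few places. The reconciliation itself calls for no new tests, visits or participants and no change to the analysis.

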7.2. Pharmacokinetics Assessments

7.2.1. Serum for Assessment of Tremelimumab Pharmacokinetics

Blood samples (approximately 3 mL whole blood) to provide a minimum of 1 mL of serum for measurement of serum tremelimumab concentrations will be collected from participants receiving tremelimumab. The samples will be collected into appropriately labeled tubes at time points outlined in the [Schedule of Activities](#). The PK sampling schedule may be modified based on emerging PK data, but the total number of PK samples will remain the same.

In addition to samples collected at the scheduled times, an additional blood sample for determination of serum tremelimumab concentration should be collected from participants experiencing unexpected and/or serious AEs and the date and time of blood sample collection and of last dosing prior to PK collection documented on the CRF.

Where noted in the [Schedule of Activities](#), blood samples for tremelimumab concentrations will be collected at approximately the same time as other assessments such as PD samples and ECGs (first ECG then PK collection), wherever possible.

All efforts will be made to obtain the PK samples at the scheduled nominal time relative to dosing. However, samples obtained within the protocol specified time window will be considered compliant with the protocol, and the exact time of the sample collection will always be noted on the CRF. If a scheduled blood sample collection cannot be completed for any reason, the missed sample time may be re-scheduled with agreement of the clinical investigator, participant, and sponsor.

PK samples will be assayed for tremelimumab using a validated analytical method at a central laboratory in compliance with Pfizer standard operating procedures (SOPs).

The PK samples must be processed and shipped as indicated in the instructions provided to the investigator site to maintain sample integrity. Any deviations from the PK sample handling procedure (eg, sample collection and processing steps, interim storage or shipping conditions), including any actions taken, must be documented and reported to the sponsor. On a case-by-case basis, the sponsor may make a determination as to whether sample integrity has been compromised. Any deviation from the specified sample handling procedure resulting in compromised sample integrity will be considered a protocol deviation.

As part of understanding the PK of the investigational product, samples may be used for evaluation of the bioanalytical method, [CCI](#)
These data will not be included in the Clinical Study Report (CSR).

7.2.2. Serum for Assessment of Sasanlimab Pharmacokinetics

Blood samples (approximately 5 mL whole blood) to provide a minimum of 2 mL of serum for measurement of serum sasanlimab concentrations will be collected from participants receiving sasanlimab. The samples will be collected into appropriately labeled tubes at time points outlined in the [Schedule of Activities](#). The PK sampling schedule may be modified based on emerging PK data, but the total number of PK samples will remain the same.

In addition to samples collected at the scheduled times, an additional blood sample for determination of serum sasanlimab concentration should be collected from participants experiencing unexpected and/or serious AEs and the date and time of blood sample collection and of last dosing prior to PK collection documented on the CRF.

Where noted in the [Schedule of Activities](#), blood samples for sasanlimab concentrations will be collected at approximately the same time as other assessments such as [CCI](#)
ECGs (first ECG then PK collection), wherever possible.

All efforts will be made to obtain the PK samples at the scheduled nominal time relative to dosing. However, samples obtained within the protocol specified time window will be considered compliant with the protocol, and the exact time of the sample collection will always be noted on the CRF. If a scheduled blood sample collection cannot be completed for

any reason, the missed sample time may be re-scheduled with agreement of the clinical investigator, participant, and sponsor.

PK samples will be assayed for sasanlimab using a validated analytical method in compliance with Pfizer standard operating procedures (SOPs).

The PK samples must be processed and shipped as indicated in the instructions provided to the investigator site to maintain sample integrity. Any deviations from the PK sample handling procedure (eg, sample collection and processing steps, interim storage or shipping conditions), including any actions taken, must be documented and reported to the sponsor. On a case-by-case basis, the sponsor may make a determination as to whether sample integrity has been compromised. Any deviation from the specified sample handling procedure resulting in compromised sample integrity will be considered a protocol deviation.

[figure not shown]
As part of understanding the PK of the investigational product, samples may be used for evaluation of the bioanalytical method, **CCI**

These data will not be included in the Clinical Study Report (CSR).

CCI

CCI

CCI

7.4. Tumor Response Assessments

Tumor assessments will include all known or suspected sites of disease. Screening images may be obtained within 5 weeks of registration. Imaging obtained as part of standard of care that are performed within 28 days (-7 days) of registration may be used for screening assessment. Imaging will include (a) CT scan (computerized tomography) of the chest, abdomen and pelvis, or magnetic resonance imaging (MRI) of these same areas, and (b) bone scan, for participants with known or suspected bone metastases. Baseline brain imaging (CT or MRI) is not required, except in the case of symptomatic participants to rule out brain metastases (see Section 4).

The same imaging technique (CT scan or MRI) used to characterize lesions identified at baseline should be employed when performing on-study tumor assessments. As the intention of administration of VBIR-2 is to activate an anti-tumor immune response in the vaccine draining lymph nodes, the inguinal (limb) and axillary (arm) lymph nodes should not be used as target lesions, since injections of antigens may be given in the upper arm or thigh. It is possible that lymph nodes draining the upper arm or thigh may become enlarged following administration of the VBIR-2, and may not accurately reflect the status of underlying disease.

Anti-tumor activity will be assessed through radiological tumor assessments conducted at baseline; during treatment as specified in the [SOA](#); whenever disease progression is suspected (eg, symptomatic deterioration); and at the time of withdrawal from treatment (if not done in the previous 6 weeks).

Assessment of response will be made using RECIST version 1.1 ([Appendix 3](#)).

All participants' files and radiologic images must be available for source verification and for potential peer review. In addition, historical images (collected up to one year prior to study entry) may be requested for potential peer review.

